**2. LIST OF ABBREVIATIONS**

ADR	Adverse Drug Reaction
AE	Adverse Event
AESI	Adverse Event of Special Interest
CRF	Case Report Form
CTP	Clinical Trial Protocol
ENCePP	European Network of Centres for Pharmacoepidemiology and Pharmacovigilance
EU-QPPV	European Union-Qualified Person for Pharmacovigilance
GPSP	Good Post-marketing Study Practice
J-RMP	Japanese Risk Management Plan
MedDRA	Medical Dictionary for Regulatory Activities
[REDACTED]	[REDACTED]
PMDA	Pharmaceuticals and Medical Devices Agency
PMS	Post Marketing Surveillance
PSUR	Periodic Safety Update Report
SAE	Serious Adverse Event
TSAP	Trial Statistical Analysis Plan

#### Medical adviser

## 4. ABSTRACT

Name of company: Boehringer Ingelheim			
Name of finished medicinal product: Prizbind® for Intravenous Solution 2.5 g			
Name of active ingredient: Idarucizumab (V03AB37)			
Protocol date: 23 Sep 2016	Study number: 1321.15	Version/Revision: 3.0	Version/Revision date: 25 Mar 2019
Title of study:	The drug use-results survey (All-Case Surveillance) on Prizbind® for Intravenous Solution 2.5 g in Japan		
Rationale and background:	
The Japanese Law for Ensuring the Quality, Efficacy, and Safety of Drugs and Medical Devices requires accumulating safety and effectiveness data of launched products in Japan for re-examination. Since there are a limited number of Japanese subjects treated in clinical trial, All-Case Surveillance is planned to collect safety and effectiveness data of Prizbind® for Intravenous Solution 2.5 g.
 
The PMS plan is a part of the local Risk Management Plan in Japan (J-RMP). The J-RMP was submitted to the Japanese regulatory authority, the PMDA as a part of J-CTD and need to be approved by PMDA as approval condition. After 8years from approval, the results of the PMS are needed to be submitted to the PMDA, as a part of the re-examination dossier.
		
Research question and objectives:	This PMS is designed to investigate the safety and effectiveness of Prizbind® for Intravenous Solution 2.5 g in patients under Japanese clinical condition according to the Japanese package insert.		
Study design:	
Non-interventional study based on newly collected data. All patients administrated Prizbind® for Intravenous Solution 2.5 g after the approval at the sites contracted with the sponsor will be registered. This study permits the contract with the sites both before and after patient's administration of Prizbind® to collect the data retrospectively. The study will consist of data from baseline visit to 4weeks follow-up for patients who initiate Prizbind® for Intravenous Solution 2.5 g. The patient registration should continue until the approval condition will be removed. CRF will not be collected after the number of cases reaches target number.
		
Population:	
Inclusion criteria
 
 
- Patients who are prescribed with Prizbind® for Intravenous Solution 2.5 g by the discretion of investigators
 
 
Exclusion criteria
 
 
- None
 
		

[figure not shown]
Name of company: Boehringer Ingelheim			
Name of finished medicinal product: Prizbind® for Intravenous Solution 2.5 g			
Name of active ingredient: Idarucizumab (V03AB37)			
Protocol date: 23 Sep 2016	Study number: 1321.15	Version/Revision: 3.0	Version/Revision date: 25 Mar 2019
Variables:	Primary outcomes Any suspected ADRs (primary outcome), Serious AEs, and AEs for important potential risks(hypersensitivity, thrombotic event) Secondary outcomes Effectiveness will be assessed with a focus on the following variable as secondary outcome. Reversal of anticoagulation as measured by coagulation test (aPTT, activated partial thromboplastin time)(secondary outcome) 		
Data sources:	Case Report Forms (CRFs) for individual patients will be provided by the sponsor. After the medical examination and observation at the specified points (Baseline, up to Week 4, or discontinuation) are completed, the investigator needs to immediately enter data of the registered patients (including withdrawals and dropouts) in CRF. In case that any adverse events occur, the data should be as soon as possible entered into CRF.		
Study size:	300		
Data analysis:	Due to the nature of the observational study, no confirmatory statistical testing is foreseen in this study. Analyses are descriptive in nature including means, standard deviation, min, Q1, medians, Q3, max, frequency and percentages.		
Milestones:	Start of data collection: 28 September 2016 End of data collection: March 2020 (in plan) Final report of study results: 4Q 2020 (in plan)		

Table 1 Flow chart

Observation / Evaluation time points are approximate. Collected data should be reported as those to the closest available time.

Item	Time	Observation period			
		Baseline before treatment	Drug administration	48 hours after administration	4 weeks/or discontinuation
Patient registration* 	X				
Patient demographics	X				
Medical history	X				
Dabigatran use	X				
Bleed assessment Surgery/Procedure		X (to be reported throughout the observation period)			
Prizbind® administration		X			
Coagulation tests* 		X (to be reported throughout the period)			
Concomitant medications /therapy		X (to be reported throughout the observation period)			
Blood pressure, pulse rate		(X )(to be reported throughout the period)		(X )(to be reported)	
Laboratory tests		(X )(to be reported throughout the period)		(X )(to be reported)	
Adverse events		X (to be reported throughout the period)			
Re-start anticoagulant therapy					X

\*1: Patients administered Prizbind® for Intravenous Solution 2.5 g after approval will be registered regardless of date of contract for this study.

\*2: All aPTT values monitored during the observation period should be entered.

(X): If applicable

**5. AMENDMENTS AND UPDATES**

Number	Date	Section of study protocol	Amendment or update	Reason
2.0	6 Jun 2018	9.3.3	Amendment	In order to harmonize the CTP and the CRF
3.0	12 Mar 2019	9.1, 11.2	Update	In order to transfer to the only-enrollment phase

## 6. MILESTONES

Milestone	Planned Date
Start of data collection	28 September 2016
End of data collection	March 2020 (in plan)
Registration in the EU PASS register	Registered
Final report of study results	4Q 2020 (in plan)

## 7. RATIONALE AND BACKGROUND

The reversal of the anticoagulant effects of dabigatran by idarucizumab, a humanised monoclonal antibody fragment, has been demonstrated in volunteers (studies 1321.1, 1321.2 and 1321.5) and patients from the Study 1321.3 (about 500 patients were enrolled in Q2 2016).

█████ participated in Global phase III study (1321.3) after phase I study (1321.5) in Japanese subjects (60 cases) was finished. For the application for marketing approval in Japan, an interim analysis of 1321.3 was conducted by using data in 243 patients (including 4 Japanese patients) as of October 26, 2015. These clinical study results showed that idarucizumab was effective for neutralizing the anticoagulant effect of dabigatran and a favorable safety profile of idarucizumab.

On the other hand, a limited number of Japanese subjects were treated in clinical trials. MHLW may require All-Case Surveillance of idarucizumab as an approval condition. Therefore, █████ plans All-Case Surveillance to collect safety and efficacy data of idarucizumab (Prizbind® for Intravenous Solution 2.5 g) after its marketing launch in Japan.

### **Japanese regulation related to Post Marketing Surveillance (PMS)**

This PMS is planned according to the Japanese Law for Ensuring the Quality, Efficacy, and Safety of Drugs and Medical Devices. The law requires in principle that data on the safety and effectiveness of all launched products to be accumulated under Japanese clinical condition. The PMS is a part of the local Risk Management Plan in Japan (J-RMP) to be submitted to the Pharmaceuticals and Medical Devices Agency (PMDA), the local regulatory agency in Japan at New Drug Application. After 8 years from approval of registration, the data collected in the PMS are required to be submitted to PMDA according to the process of re-examination.

### **Japanese regulation related to All-Case Surveillance**

The All-Case Surveillance means a use-results survey that is conducted to collect information on all patients who have used the product since its launch until a data from certain number of cases have been accumulated. The All-Case Surveillance is required for products that need the background information of patients treated with the product as well as safety and effectiveness issues related to the product for reaffirming approval details and collecting information which is essential for proper use at the earliest possible stage, thoroughly.

For example, the regulatory agency may require the implementation of the All-Case Surveillance for a pharmaceutical product as an approval condition when there are only a small number, or even no cases existing in clinical trials in Japan and when there are any concerns about the pharmaceutical product regarding the occurrence of serious adverse drug reactions. Necessity for the All-Case Surveillance is determined by the following steps: review in PMDA, subsequent discussion by the Pharmaceutical Affairs and Food Sanitation Council, and the final decision by MHLW.

## **8. RESEARCH QUESTION AND OBJECTIVES**

This PMS is designed to investigate the safety and effectiveness of Prizbind® for Intravenous Solution 2.5 g in patients under Japanese clinical condition according to the Japanese package insert.

## 9. RESEARCH METHODS

### 9.1 STUDY DESIGN

This is a non-interventional study based on new data collection to gather data on safety and effectiveness of the Prizbind® for Intravenous Solution 2.5g under Japanese clinical condition. Patients who have been treated with dabigatran etexilate and required rapid reversal of the anticoagulant effects of dabigatran enter the study. Prizbind® is given intravenously, as idarucizumab at 5 g/dose (2 x 2.5 g/50 mL).

The study will consist of data from baseline visit to 4 weeks follow-up for patients who initiate Prizbind® for Intravenous Solution 2.5 g.

The study will be initiated after the approval of Prizbind® for Intravenous Solution 2.5 g in Japan. All patients administrated Prizbind® for Intravenous Solution 2.5 g after the approval at the sites contracted with the sponsor will be registered. The study permits the contract with the sites both before and after patient's administration of Prizbind to collect the data retrospectively. CRFs of 300 patients will be collected. However the patient registration continues until the approval condition has been removed.

Information will be collected via CRFs for patients who have been administered Prizbind up to and including 14 April 2019. For patients administered Prizbind after the time point, no pre-specified information will be collected via CRFs. Following the time point, patients will only be registered in order to count the number of patients being administered Prizbind at every site, for so long as it is required by PMDA.

The primary outcome of this study is the frequency of patients with any suspected adverse drug reactions (ADRs)

The secondary outcome of this study is reversal of anticoagulation as measured by aPTT

### 9.2 SETTING

#### 9.2.1 Study sites

All sites that Prizbind® for Intravenous Solution 2.5 g administered to patients will participate in this study. The sites will be contracted with [REDACTED] A medical representative (MR) will explain the objectives and design of this study to the investigators at study sites and exchange a written contract with the head of the study site (e.g., hospital director). The sites which do not exchange a contract beforehand will be requested, when MR provides Prizbind® material including documents for this study and the package insert etc. to the sites, to inform of patient who administered Prizbind® to [REDACTED]

## **9.2.2 Study population**

### **9.2.2.1 Inclusion / exclusion criteria**

#### Inclusion criteria

- Patients who are prescribed with Prizbind® for Intravenous Solution 2.5 g by the discretion of investigators

#### Exclusion criteria

- None

### **9.2.2.2 Registration period**

From the 28 September 2016 until until the approval condition will be removed.

### **9.2.2.3 Patient registration method**

At each study site, all patients who initiate treatment with Prizbind® for Intravenous Solution 2.5 g after the approval will be registered into this study.

Paper registration form will be used to collect necessary information and will be sent to the sponsor by fax.

#### End of registration

Patient registration will be stopped after the approval condition will be removed.

Only patient registration will be continued and CRF data will not be collected after the number of cases reaches target number.

## **9.2.3 Study visits**

Collected data should be reported as those to the closest available time (see [Table 1](#)).

## **9.2.4 Study discontinuation**

█ reserves the right to discontinue the study overall or at a particular study site at any time for the following reasons:

1. Emergence of any effectiveness/safety information that could significantly affect continuation of the study
2. Violation of Good Post-marketing Study Practice (GPSP), the NIS protocol, or the contract by a study site or investigator, disturbing the appropriate conduct of the study

The study site will be reimbursed for reasonable expenses incurred in case of study termination (except in case of the second reason).

## 9.3 VARIABLES

### 9.3.1 Exposures

Dosage and administration: Prizbind® (2 x 2.5 g/50 mL) is administered intravenously, as two consecutive infusions over 5 to 10 minutes each or as a bolus injection in adults.

Exposure to Prizbind®: The total dose is 5 g (two 2.5g vials).

### 9.3.2 Outcomes

#### 9.3.2.1 Primary outcomes

Safety will be assessed with a focus on the following variables, frequencies and percentages.

- Any suspected ADRs (primary outcome)
- Serious AEs
- AEs for important potential risks\*: hypersensitivity, thrombotic event (ischemic stroke, myocardial infarction, pulmonary embolism, deep vein thrombosis, systemic embolism) \*: Immunogenicity will be assessed by clinical signs and symptoms of hypersensitivity.

How to assess and report AEs including the definitions are described in section 11.

#### 9.3.2.2 Secondary outcomes

[figure not shown]
Effectiveness will be assessed with a focus on the following variable as secondary outcome.

[figure not shown]
- Reversal of anticoagulation as measured by coagulation tests( aPTT)

The maximum effect on the anticoagulant activity within 4 hours after the completion of administration:

$$\text{Maximum Reversal : } \{ (\text{predose aPTT} - \text{minimum postdose aPTT}) / (\text{predose aPTT} - \text{ULN}) \} \times 100\%$$

ULN: upper limit of normal in each site

### 9.3.3 Covariates

#### Baseline characteristics and observation items

After the medical The following items will be considered as the baseline characteristics. For all interventions/measures dates will be recorded. (see [Table 1](#)).

##### Demographics:

- Dabigatran Use(start date, daily dose, times/day, date and time of last intake)
- Prizbind® purpose of use(life-threatening or uncontrolled bleeding, emergency surgery/urgent procedures, other)
- Bleeding location, severity, start date and time, bleeding related to trauma
- Type of surgery/urgent procedure
- In/out patient
- Gender
- Age (birth year)
- Height
- Weight
- hypersensitive disposition
- Pregnancy
- Medical history/concomitant diseases
- History of bleeding events
- Department (emergency, cardiovascular, Neurosurgery, Neurology, Gastroenterolog, other)
- Participation of dabigatran clinical trial

##### Administration of Prizbind® :

- Treatment (dose/an injection, Start date and time, end date and time, consecutive infusions or as bolus injection)
- Primary reason of discontinuation for the survey

##### Bleeding / Surgery:

- Bleeding Status (Stopped, Reduced, No change, worsened, Temporarily stopped and re-bleeding,Not assessable, time and date)
- Volume of lost Blood (if applicable)
- Surgery/urgent procedures (indication, start date and time, end date and time)

##### Coagulation test values (if applicable):

aPTT, PT-INR, Fibrinogen, FDP, D-dimer

All aPTT values monitored during the observation period should be entered.

##### Concomitant medications:

- Treatment period (Start date, end date)
- Reason for use

Concomitant therapies (use of blood products)

- blood products/transfusion (Product, Number of Unit, Treatment period)
- FFP, packed RBCs, platelets, whole blood, volume expanders, tranexamic acid, cryoprecipitate, PCCs, Factor VIIa and any other hemostatic agents
- Dialysis(Yes/no)

Blood pressure, pulse rate:

- Systolic/ diastolic blood pressure, Pulse rate

Re-start anticoagulant therapy

- Re-Start date and time
- Name of medication, dose

Laboratory tests (if applicable):

- Liver function test (ALT, AST, Total Bilirubin, Alkaline Phosphatase (ALP))
- Renal function test (BUN, Creatinine)
- Na+, K+, Cl-
- Albumin
- Plasma glucose
- Creatine kinase (CK-MB:if increased )
- Triglyceride,Cholesterol (Total)
- Hematology(White blood Cell Count, Red blood Cell Count, Hemoglobin, Hematocrit, Platelet Count)

## 9.4 DATA SOURCES

Case Report Forms (CRFs) for individual patients will be provided by the sponsor.

After the medical examination and observation at the specified points (Baseline, up to 4 weeks, or discontinuation) are completed, the investigator needs to immediately enter data of the registered patients (including withdrawals and dropouts) in CRF. In case that any adverse events occur, the data should be immediately entered into CRF.

## 9.5 STUDY SIZE

It is planned to collect 300 patients.

A sample size of 300 patients was planned in consideration of post-marketing occurrence of haemorrhagic events observed for Prazaxa® (based on the periodic safety update reports) and on the basis of feasibility.

Important potential risks (thrombosis and hypersensitivity) are considered as the key survey items. If real incidence rates of thrombosis and hypersensitivity in Japanese patients are same

as shown in the interim data in Study 1321.3 (5.3% and 12.3%) [[c03666927-01](#)], 95% confidence interval of their incidence rate is shown in the [Table 2](#).

To ensure the same accuracy of the estimation (95% confidence interval: 2.8% to 9.0% (thrombosis), 8.4% -17.1% (hypersensitivity) in this study, about 250-300 cases is required with conservative estimation. Further, with a sample size of 300 patients, any ADR with frequency of 1% or higher can be detected with probability of 95% or greater in at least one patient.

Table 2 95% confidence interval of the incidence rate

N	Incidence rate	95% confidence interval		Upper-Lower
		Lower	Upper	
Thrombosis				
100	5.30%	1.7%	11.8%	10.1%
150	5.30%	2.2%	10.3%	8.1%
200	5.30%	2.6%	9.4%	6.8%
250	5.30%	2.9%	8.9%	6.0%
300	5.30%	3.0%	8.5%	5.5%
350	5.30%	3.2%	8.2%	5.0%
400	5.30%	3.3%	8.0%	4.7%
Hypersensitivity				
100	12.30%	6.5%	20.5%	13.9%
150	12.30%	7.5%	18.7%	11.2%
200	12.30%	8.1%	17.7%	9.6%
250	12.30%	8.5%	17.0%	8.6%
300	12.30%	8.8%	16.6%	7.8%
350	12.30%	9.0%	16.2%	7.2%
400	12.30%	9.2%	15.9%	6.7%

## 9.6 DATA MANAGEMENT

Data management is going to be outsourced to CRO(s). Detailed data management process with the CRO(s) will be described as data management procedure (or plan) which will be approved by BI-TDM and the CRO(s) before the initiation of DM operations. Data management and statistical software(s) are to be determined with the CRO(s) and described in the procedure (or plan).

Paper-based case report form is used for 1321.15 and monitoring is not applicable for PMS in Japan.

	Contract research organizations
Name	

## 9.7 DATA ANALYSIS

This is a non-interventional study based on new data collection to gather data on safety and effectiveness of the Prizbind® for Intravenous Solution 2.5 under Japanese clinical condition. Analyses for safety, effectiveness and baseline characteristics are descriptive in nature including means, standard deviation, min, Q1, medians, Q3, max, frequency and percentages.

Per local regulation, any patient who meets at least one of the following criteria is treated as ineligible for all analyses:

- No follow-up visit data are available
- No required registration procedure is followed
- No valid site contract is available

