3. INTRODUCTION

The purpose of this document is to provide a more technical and detailed elaboration of the principal features of the analysis described in the protocol, and to include detailed procedures for executing the statistical analysis of the primary and secondary variables and other data.

This TSAP assumes familiarity with the Non-interventional Study (NIS) protocol, including Protocol Amendments. In particular, the TSAP is based on the planned analysis specification as written in NIS protocol Section 9.7 “DATA ANALYSIS”. Therefore, TSAP readers may consult the NIS protocol for more background information on the study, e.g., on study objectives, study design and population, treatments, definition of measurements and variables, planning of sample size.

SAS® Version 9.4 will be used for all analyses.

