4. CHANGES IN THE PLANNED ANALYSIS OF THE STUDY

There has been no change in the planned analysis from the statistical methods described in the NIS protocol.

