6.2 IMPORTANT PROTOCOL VIOLATIONS

The following table defines the different categories of important PVs. The right-most column describes which PVs will be used to exclude patients from the different patient analysis sets. The final decision about which patients will be excluded from analysis sets will be taken during the course of the study and at report planning meetings before database lock at the latest.

Table 6.2: 1 Important protocol violations

Category / Code		Description	Requirements	Detection method	Excluded from
A		Entrance criteria not met			
	A1	Off-label use	Reason of use is “Other” only.	Automated	Effectiveness
	A2	No treatment with Prazaxa		Automated	Effectiveness
B		Trial medication			
	B1	No treatment with Prizbind		Automated	Safety
C		Missing data			
	C1	No all effectiveness data	There is none of following effectiveness data:a pair of predose/postdose aPTT, date/time of hemostasis, bleeding category and information about re-start anticoagulant therapy	Automated	Effectiveness
D		Trial specific			
	D1	Duplicated registration	In different patient number, sex, birthday, start date of first administration of Prizbind, height, weight and site name are the same.	Manual	Safety
	D2	Registration rule not followed	See the NIS protocol Section 9.2.2.2 and 9.2.2.3	Manual	Safety
	D3	Site contract is not valid		Manual	Safety

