6.3 SUBJECT SETS ANALYSED

The safety set will be the basis of all demographic, baseline and safety analyses. Effectiveness analysis will be on basis of the effectiveness set.

- Safety set:

[figure not shown]
This patient set includes all patients who had no invalid registration, who were documented to have taken at least one dose of Prizbind.

[figure not shown]
- Effectiveness set:

[figure not shown]
This patient set includes all patients with Prizbind in the safety set who have at least one available effectiveness data.

[figure not shown]
Table 6.3: 1 Subject sets analyzed

Class of endpoint	Subject set								
	Safety set					Effectiveness set			
	All	Group A	Group B	Group A+B	Other	All	Group A	Group B	Group A+B
Primary endpoints	X								
Secondary endpoint					X				
Disposition	X								
Demographic and baseline characteristics									
Medical history/concomitant diseases									
Concomitant medication	X								
Concomitant therapies									
Baseline coagulation test									
Treatment exposure									
Termination of PMS									
Bleeding assessment	X				X				
Surgery / invasive procedure assessment		X			X				

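### The protocol bars patients with no follow-up visit data from every analysis; the SAP safety set keeps them, so the two documents give different denominators for the primary ADR rate

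*Protocol*

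**What the plan says.** Protocol Section 9.7, citing local regulation, states that "any patient who meets at least one of the following criteria is treated as ineligible for all analyses". The three criteria are that "No follow-up visit data are available", that the required registration procedure was not followed, and that there is no valid site contract. Protocol Section 9.7.1 applies these criteria to the safety analysis by cross-reference and also requires that a CRF was collected.

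The SAP introduction says that "the TSAP is based on the planned analysis specification as written in NIS protocol Section 9.7", and SAP Section 4 adds: "There has been no change in the planned analysis from the statistical methods described in the NIS protocol". SAP Table 6.2:1 excludes patients from the safety set under D2, "Registration rule not followed", and D3, "Site contract is not valid", and also under B1 (not treated) and D1 (duplicate registration). Its only missing-data code is C1, "There is none of following effectiveness data", which excludes from the effectiveness set alone. SAP Section 6.3 defines the safety set thus: "This patient set includes all patients who had no invalid registration, who were documented to have taken at least one dose of Prizbind".

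SAP Section 7.8 runs all safety analyses on that set. By default, SAP Section 7 takes percentages over every patient in the set, including those with missing values.

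**The concern.** The primary outcome in Protocol Section 9.1 is the frequency of patients with any suspected ADR, so the rule that decides who is in the denominator is part of its definition. The protocol removes a patient for whom nothing was observed after dosing. The SAP keeps that patient, and because no ADR can have been recorded, the patient counts as a non-event. Two analysts, each following one document correctly, could report different primary percentages. The same set carries the demographic and baseline tables (SAP Section 6.3) and the subgroup odds ratios (SAP Section 7.8.1).

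Such patients are plausible. Protocol Section 9.9 names loss to follow-up as a limitation, and also missing information at sites contracted after administration. SAP Section 6.6 fills in a missing end of follow-up from the last date in the CRF; it does not remove the patient.

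**Working it through.** **Step 1. Set the criteria side by side.**

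| Protocol 9.7 criterion (ineligible for all analyses) | Code in SAP Table 6.2:1 | Excluded from |
|---|---|---|
| No follow-up visit data | none | – |
| Registration procedure not followed | D2 | Safety |
| No valid site contract | D3 | Safety |

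The codes run A1, A2, B1, C1, D1, D2, D3 without a gap, and the safety-set sentence in SAP 6.3 is complete. A blacked-out code is therefore an unlikely explanation.

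**Step 2. Follow one patient through both documents.** Take a patient who is validly registered at a contracted site, has one documented dose, and has no post-dose entry in the CRF. Under Protocol 9.7 and 9.7.1 the patient is in neither numerator nor denominator. Under SAP 6.3 and 7 the patient is in the denominator and not in the numerator.

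**Step 3. Reproduce the plan's own figures at N = 300 (Protocol Section 9.5).** The probability of seeing at least one case of an ADR with true frequency 1% is 1 − 0.99^300 = 1 − 0.04904 = 0.9510, which agrees with the stated 95% or greater. Exact (Clopper-Pearson) 95% intervals, with x = rate × 300 left unrounded, are 3.1% to 8.5% at 5.3% and 8.8% to 16.6% at 12.3%. Table 2 gives 3.0% to 8.5% and 8.8% to 16.6%. The figures reproduce to within 0.1 point.

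The detection statement has almost no slack. At N = 299 the probability is 0.9505. At N = 298 it is 1 − 0.04904/0.99² = 1 − 0.05004 = 0.94996, just under 95%. At N = 285 it is 0.9430. If 300 is the count before exclusions, removing two patients under the protocol rule already takes it below the stated level.

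**Step 4. Size of the difference.** The documents give neither an expected ADR rate nor the number of patients without post-dose data, so both are assumed. Let x patients have the event and k of the 300 have no post-dose record. The SAP rate is x/300 and the protocol rate is x/(300 − k). The numerator is the same because an unobserved patient cannot contribute a recorded event. The ratio of the two rates, 300/(300 − k), is 1.0101, 1.0204 and 1.0526 for k = 3, 6 and 15.

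| Events x | SAP, x/300 | Protocol, k = 3 | k = 6 | k = 15 |
|---|---|---|---|---|
| 15 (assumed) | 5.0% | 5.1% | 5.1% | 5.3% |
| 30 (assumed) | 10.0% | 10.1% | 10.2% | 10.5% |
| 60 (assumed) | 20.0% | 20.2% | 20.4% | 21.1% |
| 16 (about the Table 2 thrombosis rate) | 5.3% | 5.4% | 5.4% | 5.6% |
| 37 (about the Table 2 hypersensitivity rate) | 12.3% | 12.5% | 12.6% | 13.0% |

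SAP Section 7 reports percentages to two decimals, so even one such patient would show: 30/300 = 10.00% against 30/299 = 10.03%.

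**Step 5. Sensitivity to the undefined term.** Neither document defines follow-up visit data. Suppose it meant only the later time points of Protocol Table 1, and 15 patients were excluded of whom 3 had early events. Thrombosis would then go from 16/300 = 5.33% to 13/285 = 4.56%, and hypersensitivity from 37/300 = 12.33% to 34/285 = 11.93%. Under that reading the protocol rate can be the lower one.

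**The case against.** The SAP is not a stand-alone document: it presumes knowledge of the protocol and says it builds on Section 9.7. SAP Section 6.2 leaves final exclusions to decisions during the study and at meetings before database lock, so the protocol rule could still be applied. The no-change statement refers to statistical methods, which need not include eligibility for a set. Protocol Section 9.4 has the CRF completed after up to 4 weeks or at discontinuation, including for withdrawals and dropouts, so a CRF with no post-dose entry would be unusual. The assumed effects are small beside the Table 2 interval widths at N = 300 (5.5 and 7.8 points), and no confirmatory test depends on them. Part of the specification, such as the ADS plan, cannot be seen.

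The points about size stand: the number affected is unknown, may be zero, and any effect is probably small. It also stands that the term is undefined and that the direction of the effect depends on its reading.

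The rest does not remove the contradiction. The meeting would work from a table whose last column says which violations exclude from which set, and no row covers this case. Writing out two of three criteria makes it hard to read the third in by reference. The population for the primary outcome is specified in the very protocol section that the SAP says it implements, so a no-change statement should hold for it. A patient with no post-dose data at all lacks follow-up visit data on any reading, so for that patient the two documents do disagree.

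**Conclusion.** The concern holds: the plan is wrong as written. The SAP drops one of the protocol's three grounds for ineligibility from its safety set and declares no change. For patients with no post-dose record, keeping them as ADR-free can only lower the reported rate. In the illustrations with 3 to 15 such patients among 300, a 10.0% rate under the SAP corresponds to 10.1% to 10.5% under the protocol, and a 20.0% rate to 20.2% to 21.1%. These sizes rest on assumed counts and on reading the criterion as no post-dose record. Confidence is high in the textual mismatch. Whether any patient is affected is unknown. It should be corrected because it concerns the primary denominator and costs almost nothing; it does not threaten the study's conclusions.

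**What to change.** Choose one of two routes.

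1. Add a code to SAP Table 6.2:1 that excludes from the safety set patients with no post-dose record in the CRF. State that any post-dose record, including an AE or a death, counts as follow-up data. This definition fits Protocol Section 9.2.3 (report at the closest available time), Section 9.4 (data entered for withdrawals and dropouts) and Section 11.2 (fatal events collected). It also prevents early events from being removed along with the patient.
2. If the sponsor confirms that local regulation does not require this exclusion for safety, keep these patients and declare the departure from Protocol Section 9.7 in SAP Section 4.

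In either case, report the number of patients affected, by reason, in the disposition table. As a point of wording, add the collected-CRF condition of Protocol Section 9.7.1 to the safety set in SAP Section 6.3.

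The cost is one code with its definition, or one sentence in SAP Section 4, plus one disposition row. No new data are needed.
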